SPONSORED RESEARCH AND COLLABORATION AGREEMENT
BETWEEN 7D SURGICAL, INC. AND HOSPITAL FOR SPECIAL SURGERY

(This is Addendum 1 to that certain Sponsored Research and Collaboration Agreement (SRCA) between the parties dated November 20, 2017, and this Addendum is subject to the terms of that SRCA, including but not limited to all the rights and obligations of the parties stated in such SRCA.)

ADDEDENDUM 1

A Single Center, Cohort Study Of The MvIGS Spine Navigation System

Addendum Approved:

Hospital for Special Surgery

By: _____

Name: [name]

Title: VP, Research Administration

Date: _____

7D Surgical, Inc.

By: _____

Name: _____

Title: _____

Date: _____

Read, acknowledged and agreed:

By: _____

Name: [name], MD, FACS

Title: Chief Emeritus, Spinal Surgical Service

Principal Investigator

Date: _____

7D Surgical Protocol

A Single-Center, Cohort Study of the MvIGS Spine Navigation System

Protocol Approval Date:

March 2, 2018

Sponsor

7D Surgical
[name]
[name]
Canada

Confidentiality Statement

This document is a confidential communication of 7D Surgical. The recipient agrees that no information contained herein will be published or disclosed without 7D Surgical's written approval. This document may be disclosed to appropriate institutional review boards, independent ethics committees, or duly authorized representatives of regulatory authorities as appropriate; under the condition that confidentiality is requested.

EU CLINICAL STUDY PROTOCOL SYNOPSIS

Sponsor: 7D Surgical

Product: Machine-vision Image guided Surgery Navigation System

Title of Study: "A Single-Center, Prospective Cohort Study of the MvIGS (MvIGS) Spine Navigation System"

Number of Centers Planned: 1

Planned Study Period: 1Q2018-1Q2019

Primary Objective: To prospectively investigate clinical outcomes following implementation of the Machine-vision Image Guided Surgery (MvIGS) spine navigation system in patients requiring posterior instrumentation.

General Design and Methodology: This is a single center, prospective, non-randomized cohort study to assess clinical outcomes following the use of the MvIGS spine navigation system for treatment of spinal stenosis and degenerative spondylolisthesis of the lumbar spine. There will be separate study arms for cases utilizing the three-dimensional (3D) MvIGS spine navigation system and cases that utilize conventional two-dimensional (2D) fluoroscopy.

Study Arm 1: One, two and three-level posterior spine fusion surgery using bilateral pedicle screw instrumentation under 3D MvIGS intraoperative navigation guidance.

Study Arm 2: One, two and three-level posterior spine fusion surgery using bilateral pedicle screw instrumentation under 2D fluoroscopy.

Primary Endpoint: The primary endpoint is based on the mean reduction in total length of operative time. Operative time will be determined by the official recorded operative notes.

Secondary Endpoints: Secondary endpoints include:

- Length of stay
 - Aim: Decrease length of hospital stay
 - Measured: Time (Hours)
- Length of time for initial image processing
 - Aim: Decrease disturbance to surgeon workflow
 - Measured: Time (Minutes)
- Length of time to place all screws
 - Aim: Reduce the time for screw placement
 - Measured: Time (Minutes)
- Length of time to confirm screw placement
 - Aim: Reduce the time needed for confirmation of screw location
 - Measured: Time (Minutes)
- Length of time to register images
 - Aim: To reduce time for registration of reference images
 - Measured: Time (Seconds)
- Estimated Blood Loss (EBL)

- Aim: To reduce the EBL of each case
 - Measured: Milliliters (mL)
- Incidence of Malalignment
 - Aim: To decrease the incidence of pedicle screw malalignment
 - Measured: Misalignment angle between pilot hole and screw trajectory (degrees)
- Complications: Neurological Deficits, Dural Tears, deep wound infections, etc.
 - Aim: To decrease the incidence of intraoperative complications
 - Measured: number of reported complications while hospitalized
- Measurement of 2D fluoroscopy radiation exposure
 - Aim: to reduce patient and surgeon exposure to radiation
 - Measured: Exposure measured by Dose Area Product (DAP)

Exploratory Analyses: Exploratory analyses include the number of vertebral levels involved, radiographic evaluations of anterior disc height, implant migration, and stability, and preservation of motion at the adjacent, un-instrumented level.

Number of Patients Planned: A total of 130 patients, with 65 patients per group.

Criteria for Inclusion: Patients are included in the study if all of the following criteria are met:

- 1) Diagnosis of spinal stenosis of the lumbar spine with \leq grade 2 degenerative spondylolisthesis
- 2) Skeletally mature adults between the ages of 18-85 years at the time of surgery;
- 3) Has completed at least 6 months of conservative therapy;
- 4) Personally signed and dated informed consent document prior to any study-related procedures indicating that the patient has been informed of all pertinent aspects of the study.

Criteria for Exclusion: Patients are excluded from participating in this study if any of the following criteria are met:

- 1) Gross instability, defined as > 3 mm translational motion on flexion/extension studies;
- 2) Degenerative spondylolisthesis $>$ grade 2
- 3) Degenerative scoliosis $> 10^\circ$ at any level in lumbar spine;
- 4) Congenital lumbar spinal stenosis;
- 5) Endplate changes;
- 6) Visible change in disc height;
- 7) Radiographic confirmation of facet joint disease or degeneration;

- 8) Prior surgery at any lumbar level including the level being treated except for: Lamino/Foraminotomy, Microdiscectomy, IDET, and Percutaneous Discectomy;
- 9) Any evidence of a prior/current fracture, compromised vertebra, current or past trauma, or tumor at affected level or the spinous processes at the adjacent levels;
- 10) Requires destabilizing surgical decompression that adversely affects the functioning of the facets;
- 11) Cauda equina syndrome defined as neural compression causing neurogenic bowel (rectal incontinence) or bladder dysfunction (bladder retention or incontinence);
- 12) Significant peripheral neuropathy or acute denervation secondary to radiculopathy, caused by conditions other than spinal stenosis;
- 13) Significant peripheral vascular disease (diminished dorsalis pedis or tibial pulses);
- 14) Morbid obesity, defined as BMI $> 40 \text{ kg/m}^2$;
- 15) Active systemic or local infection;
- 16) Active Hepatitis (receiving medical treatment within two years);
- 17) Immunocompromised such as but not limited to Acquired Immunodeficiency Syndrome (AIDS), HIV infection, Severe Combined Immunodeficiency Syndrome, Thymic Hypoplasia;
- 18) Insulin dependent diabetes mellitus or any other medical condition(s) that would represent a significant increase in surgical risk or interfere with normal healing;
- 19) Immunologically suppressed, or has received systemic steroids, excluding nasal steroids, at any dose daily for > 1 month within last 12 months;
- 20) History of Paget's disease, osteomalacia, or any other metabolic bone disease;
- 21) Active malignancy. A patient with a history of any invasive malignancy (except non-melanoma skin cancer), unless treated with curative intent and there has been no clinical signs or symptoms of the malignancy > 5 years;
- 22) Involved in study of another investigational product that may affect outcome;
- 23) Women who are pregnant, lactating or anticipate becoming pregnant within 24 months post-surgery;
- 24) Patients who are incarcerated;
- 25) Worker's compensation cases;
- 26) Patients involved in active litigation relating to his/her spinal condition;

Duration of Follow-up: Patients will be clinically followed throughout the course of their hospital admission.

1 INTRODUCTION

1.1 Background Information

Medicine and technology have long enjoyed a symbiotic relationship whereby the success of one directly advances the other. In the past few decades, innovations in surgical equipment have dramatically enhanced proficiency and improved patient safety in the operating room, thus leading to precipitous reductions in complication rates. In spine surgery, where the inherent risks are great, recent advancements in pre and intraoperative imaging technology have been heavily relied upon for guidance in complex cases. Improvements from two-dimensional (2D) plain radiographs to three-dimensional (3D) real-time imaging have given surgeons accessible accuracy in multiple planes of vision. Though there are many advantages to intraoperative imaging, there exist a number of drawbacks that have been extensively studied, most notably radiation exposure to both surgeon and patient and prolongation of operative time. In hopes to eliminate these drawbacks, an emergent technology in intraoperative spine navigation imaging, and the focus of this study, emits no radiation while simultaneously integrating into the surgeon driven workflow of the operating room.

1.2 Treatment Options

Currently, there are a number of intraoperative imaging options available to aid spine surgeons. By far, the most commonly used modality is 2D fluoroscopy. A worldwide survey conducted in 2013 by Hartl et al. reported that 78% of surgeons utilize routine fluoroscopy during spine surgery as either a control at the end of a procedure or for active monitoring used throughout the procedure. Two dimensional anterior/posterior (AP) and lateral fluoroscopic views provide reasonable accuracy measurements but also subject the patient and surgeon to additional ionizing radiation exposure and increased operative timing.

Computer assisted spine surgery is another imaging modality that has grown popular since its advent in the early 1990's (Kalfas et al.). In computer assisted cases, surgeons are provided with patient specific and real-time three-dimensional (3D) images. Spine navigation systems typically integrate recently acquired pre-operative computer-tomography (CT) images with proprietary software to help orient the surgeon through real-time 3D reconstructed images. Numerous studies have shown a significant reduction in pedicle screw malalignment rates in cases where spine navigation systems are used versus conventional 2D fluoroscopic imaging, thus confirming an increase in accuracy (Patel et al, Hartl et al, 2012). Despite this reduction in pedicle screw malalignment, spine navigation imaging systems do have inherent drawbacks. As is common in most new technologies, the computer assisted surgery (CAS) systems are more expensive than 2D fluoroscopy. CAS systems also require the use of proprietor specific probes and tools during surgery and, therefore, subject the surgeon to a learning curve that initially may prolong operative times. It was that projected disturbance in workflow that Hartl et al. reported as the reason nearly 80% of surgeons did not use CAS more frequently.

In an effort to address the growing concerns of current computer assisted spine navigation systems, an emergent technology has been developed that does not require intraoperative

ionizing radiation exposure. In addition to sparing the patient and surgeon to radiation exposure, this new spine navigation system, named the Machine-vision Image Guided Surgery (MvIGS) system, is also projected to not increase mean operative. By use of Instant Flash™ registration, localizing reference images are generated in a matter of seconds, as opposed to minutes, and thereby mitigate the disturbance to normal surgeon-defined workflow.

1.3 Name of the Device and Intended Use

The name of the device is the Machine-vision Image Guided Surgery (MvIGS) spine navigation system. The intended use of this device is to provide patient specific high quality intraoperative imaging with no radiation exposure. Use of the proprietary integrated surgical light with embedded tracking technology and Instant Flash™ registration allows for continuous and direct visualization of the surgical field with no disturbance to surgeon workflow.

1.4 Objective of Study

The main objective of this study is to prospectively compare operative time of patients requiring posterior instrumentation utilizing the MvIGS spine navigation system to patients requiring posterior instrumentation under the guidance of conventional 2D fluoroscopy.

1.5 Clinical Study Rationale

Posterior fixation is the standard of care for spinal instability and deformity. Of paramount importance are the accurate placement of transpedicular screws and the avoidance of adjacent neurovascular structures. Intraoperative 3D navigation systems are becoming increasingly popular yet conventional 2D fluoroscopy remains the more widely used modality (Hartl). Worldwide consensus from 677 spine surgeons reported the need for more data regarding surgical precision, operative time and radiation exposure, among other factors, for computer-assisted surgery (CAS) to become more widely accepted.

The purpose of this study is to evaluate the use of the MvIGS spine navigation system for pedicle screw fixation guidance and its effect on the length of operation. It is projected that the length of operation will remain similar to cases where conventional 2D fluoroscopy is utilized.

2 CLINICAL ASSESSMENTS

2.1 Primary Endpoint

The primary endpoint is based on the mean reduction in total length of operative time. Operative time will be determined by the official recorded operative notes.

2.2 Secondary Endpoints

- Length of stay
 - Aim: Decrease length of hospital stay
 - Measured: Time (Hours)
- Length of time for initial image processing
 - Aim: Decrease disturbance to surgeon workflow
 - Measured: Time (Minutes)
- Length of time to place all screws
 - Aim: Reduce the time for screw placement
 - Measured: Time (Minutes)
- Length of time to confirm screw placement
 - Aim: Reduce the time needed for confirmation of screw location
 - Measured: Time (Minutes)
- Length of time to register images
 - Aim: To reduce time for registration of reference images
 - Measured: Time (Seconds)
- Estimated Blood Loss (EBL)
 - Aim: To reduce the EBL of each case
 - Measured: Milliliters (mL)
- Incidence of Malalignment
 - Aim: To decrease the incidence of pedicle screw malalignment
 - Measured: Misalignment angle between pilot hole and screw trajectory (degrees)
- Complications: Neurological Deficits, Dural Tears, deep wound infections, etc
 - Aim: To decrease the incidence of intraoperative complications
 - Measured: number of reported complications while hospitalized
- Measurement of 2D fluoroscopy radiation exposure
 - Aim: to reduce patient and surgeon exposure to radiation
 - Measured: Exposure measured by Dose Area Product (DAP)

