3.3 Outcome Measures Recorded During the Study

Time point measurements in surgery, including total operative length, will be recorded on the day of surgery. Radiographic measurements of the misalignment angle will be retrospectively recorded and analyzed.

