3.6 Description of MvIGS Spine Navigation System

3.6.1 Materials

The equipment includes:

1. Proprietary imaging software
2. Integrated surgical light with embedded tracking technology
3. Cart with Arm and Head attachments
4. Surgical Instruments: reference clamp, awl tip, and pedicle probe

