3.6.2 Intended Use of the Device

The MvIGS spine navigation system is intended for spatial positioning and orientation of surgical instruments during pedicle screw implantation in patients undergoing posterior fixation in single or multiple levels. The surgical light is intended to be the sole luminaire during image guided surgery.

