4.2 Data Analysis

Data analysis of the study will include:

Descriptive statistics will report means and standard deviations for continuous variables of the study population. Frequencies and percentages will be used to report all discrete variables. Tests of normality for continuous variables will be evaluated using Shapiro-Wilks tests. For those that are non-parametric, Mann-Whitney U tests will be used.

Analysis of the primary outcome will use independent samples t-tests to compare the mean length of surgery between the two study arms.

Comparison of secondary outcomes between patients who undergo posterior spine fusion surgery using 2D fluoroscopy versus those who undergo the same procedure under 3D MvIGS intraoperative navigation guidance will use independent samples t-tests to analyze length of hospital stay; time for initial image processing; time to place all pedicle screws; time to confirm screw placement; time to register images; estimated blood loss; and amount of radiation exposure. Chi-square (or Fisher's exact) tests will be used to compare differences in incidence of malalignment and rate of complications between the two study groups.

To adjust for any potential confounding, multivariable regression models will be generated to report the adjusted effect of which spine navigation technique is used on length of surgical time.

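### The malalignment endpoint compares the screw with its own pilot hole, so as worded it does not measure screw placement relative to the pedicle, and the event to be tested has no cut-off.

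*Combined protocol and SAP*

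**What the plan says.** Section 2.2 (and the Synopsis, in the same terms) lists incidence of malalignment among nine secondary endpoints. Its aim is "To decrease the incidence of pedicle screw malalignment". Its measure is "Misalignment angle between pilot hole and screw trajectory (degrees".

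Section 3.3 says how the angle is obtained: "Radiographic measurements of the misalignment angle will be retrospectively recorded and analyzed". It names no modality, time point or anatomical reference.

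Section 4.2 says how it is analysed. Chi-square (or Fisher's exact) "tests will be used to compare differences in incidence of malalignment and rate of complications between the two study groups". No number of degrees is given that would turn an angle into an event.

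Two background sections show what the protocol means by accuracy. Section 1.5 states: "Of paramount importance are the accurate placement of transpedicular screws and the avoidance of adjacent neurovascular structures". Section 1.2 reports a "significant reduction in pedicle screw malalignment rates in cases where spine navigation systems are used" and takes this as confirming greater accuracy.

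**The concern.** The aim and the measure refer to different things. Placement in the sense of sections 1.2 and 1.5 concerns where the screw lies in relation to the pedicle and the structures next to it. The stated measure concerns where the screw lies in relation to the hole made for it. Final position depends on both the hole and how well the screw follows it, and the measure sees only the second.

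A reader of the results would naturally take a malalignment comparison between navigation and fluoroscopy as evidence on accuracy. If the arms differed in hole placement, in either direction, this endpoint would not register it. A finding of no difference could then be misread as equal accuracy, and a finding of a difference could be misread as better or worse placement.

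**Working it through.** **The plan's own calculation.** The documents contain one calculated figure, the power for operative time in section 4.1. Inputs: margin 40 min, assumed difference 5 min, SD 70 min, 65 per group, alpha 0.05.

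- Standard error = 70 × √(2/65) = 12.28 min.
- Noncentrality = (40 − 5)/12.28 = 2.85.
- Noncentral t, 128 degrees of freedom, one-sided 0.05: power 0.883.

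This matches the stated 0.883. It has no bearing on malalignment, for which the plan gives no rate, cut-off, number of screws or power.

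**Is there an anatomical reference anywhere?** I looked for a reference to the pedicle axis, the pedicle border, a breach grade or a planned trajectory.

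- Section 2.2 and the Synopsis: the reference is the pilot hole.
- Section 3.3: the angle is read from radiographs, with no reference stated.
- Synopsis, Exploratory Analyses: disc height, implant migration, stability and adjacent-level motion, but not screw position in the pedicle.
- Section 4.2: an incidence, with no definition of the event.

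None supplies one.

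**What the measure responds to.** Let *h* be the direction of the hole, *s* the direction of the screw and *r* the intended anatomical direction, all as unit vectors.

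- Protocol's angle = arccos(*s·h*).
- Angular placement error = arccos(*s·r*).

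If the screw follows its hole, *s* = *h*, so the protocol's angle is arccos(1) = 0 whatever the angle between *h* and *r*.

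For a screw that wanders from its hole, I used an assumed scatter of 2 degrees SD on each of two axes and 200,000 simulated screws per case. The hole errors are also assumptions, since the documents give none.

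| Assumed hole error (degrees) | Protocol's angle, screw follows hole | Placement error, screw follows hole | Mean protocol's angle, with scatter | Mean placement error, with scatter |
|---|---|---|---|---|
| 0 | 0.00 | 0.00 | 2.50 | 2.50 |
| 5 | 0.00 | 5.00 | 2.50 | 5.42 |
| 10 | 0.00 | 10.00 | 2.50 | 10.20 |
| 15 | 0.00 | 15.00 | 2.50 | 15.14 |

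A hand check on the last column: for hole error δ and per-axis scatter σ, with δ clearly larger than σ, the mean placement error is about δ + σ²/(2δ). This gives 5 + 4/10 = 5.40, 10 + 4/20 = 10.20 and 15 + 4/30 = 15.13, in line with the simulation.

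The protocol's angle is the same in every row. It carries information about scatter around the hole and none about the hole.

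**Parallel offset.** If the whole track is shifted sideways without tilting, *s* = *h* = *r* and the protocol's angle is again 0. An angle to the pedicle axis would also be 0 in that case, so only a measure of position detects a shift.

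**Measure against test.** Section 2.2 gives a continuous quantity in degrees, while section 4.2 applies a test for counts. Without a cut-off, the number of malaligned screws or patients in each arm is not defined.

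**The case against.** The strongest reply is that the wording may be loose. The plan never defines the pilot hole. If the sponsor meant a planned trajectory, a clarification would be enough. The documents do not say this, however, so the endpoint has to be judged as written, and the clarification would itself be a correction.

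It is also fair to say that the point is limited in weight. Section 1.4 makes operative time the main objective, and the sentence in section 1.5 describes posterior fixation in general. Neurological deficits and dural tears are counted during the admission, so harmful misplacement would not go wholly unrecorded. That stands, but such events are only indirect evidence on screw position.

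A reader might infer more than the documents support, in four ways:

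- **That the endpoint skips exactly the step the device guides.** Section 3.6.1 lists "Surgical Instruments: reference clamp, awl tip, and pedicle probe" and no screwdriver. But the list does not say what each tool does, and it need not be complete. Section 3.6.2 describes the device as "intended for spatial positioning and orientation of surgical instruments during pedicle screw implantation", which can cover screw insertion. The mismatch does not depend on this: a screw-to-hole angle ignores hole error however the hole was made.
- **That the comparison is pulled toward no difference.** This would need the arms to differ only in hole placement and not in how well screws follow their holes. The plan gives no information on either.
- **That the hole cannot be seen on a later film.** Section 3.3 does not name the imaging, so this cannot be judged.
- **That the study can say nothing about accuracy.** The documents support only the narrower statement that this endpoint, as worded, does not measure placement relative to the pedicle.

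**Conclusion.** The stated measure does not answer the stated aim. For a screw that follows its hole the recorded angle is 0 degrees whatever the error of the hole. For a screw that deviates, the angle is above 0 but reflects only that deviation. This follows from the definition. The particular sizes of 5, 10 and 15 degrees and the 2-degree scatter are illustrations and say nothing about how often such errors occur. No effect on the between-arm result can be computed, because the plan gives no malalignment rate, cut-off or screw count.

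The missing cut-off is a separate gap that would remain even if the reference were put right.

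The endpoint definition should be corrected before the images are read. It is one secondary endpoint, and nothing here touches the primary endpoint, its analysis or the 65 per group.

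**What to change.** In section 2.2 and the Synopsis, define malalignment as the screw's trajectory or position relative to the pedicle. Position is the better choice where the images allow it, because an angle alone misses a parallel offset. Read it on the radiographs already to be measured under section 3.3, and name their modality and time point there.

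In section 4.2, state one prespecified cut-off and whether the unit is the screw or the patient. Each patient receives several screws, so a per-patient rule fits the planned chi-square or Fisher's exact test directly. A per-screw rule needs an analysis that allows for screws within a patient.

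Keep the pilot-hole angle as a descriptive measure. If a planned trajectory was meant, correct the wording to say so; the cut-off and the unit are still needed.

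The cost is a revised definition, a revised reading form and one added rule in the analysis section, with no change in patient numbers. The downside is that the available radiographs may detect breaches of the pedicle border poorly. If they cannot support the measure, add no imaging. Instead, limit the endpoint's claim to agreement between screw and hole and make no claim about accuracy from it.
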